1.1. Prevalence of Peripheral Artery Disease and Impact

Peripheral artery disease (PAD), defined as atherosclerotic narrowing or occlusion of at least one peripheral artery, affects > 200 million people worldwide and is associated with substantial morbidity and healthcare costs.¹⁻³ Though patients may develop atherosclerotic vascular disease in any peripheral vascular bed – cerebrovascular, mesenteric, upper extremity, lower extremity – symptomatic PAD most often involves the lower extremity, and most often presents as intermittent claudication. Intermittent claudication is characterized by leg soreness or heaviness with ambulation, and often causes substantial functional limitation.⁴ Though a minority of patients with peripheral artery disease have classic intermittent claudication, a greater proportion have lower extremity symptoms, and even those who do not report claudication may have substantial unrecognized functional limitation.^{4,5}

1.2. Supervised Exercise for Peripheral Artery Disease

Pivotal clinical trials in patients with intermittent claudication showed that supervised treadmill exercise improved walking performance and functional capacity. In a meta-analysis of these trials, which included 25 studies enrolling a total of 1054 patients, supervised treadmill exercise, as compared with observational control, increased maximum walking distance by 180 meters and pain-free walking distance by 125 meters.⁶ Supervised treadmill exercise also improves six-minute walk distance and subjective measures of quality of life and functional capacity. Based on these trials, supervised treadmill exercise is a class IA recommendation in the American Heart Association/American College of Cardiology and Society for Vascular Surgery clinical practice guidelines.^{7,8}

Supervised treadmill exercise programs are characterized by several features. Patients attend sessions in person 3 times per week, and walk on a treadmill while supervised by an exercise physiologist. Sessions initially last 15 minutes, with a goal of increasing to 45 or 50 minutes by the end of the program. Classically, exercise is high-intensity, and the treadmill's pace and angle is set so that patients develop near maximal or maximal leg pain while exercising. A typical supervised treadmill exercise program lasts 6 months. More recent data has challenged this paradigm: In a meta-regression of 25 supervised treadmill exercise trials, programs designed to produce only mild claudication pain, or even to allow patients to walk at their own pain-free pace, led to the similar improvements in maximum and pain-free walking distance compared with higher intensity programs, and programs lasting 12-26 weeks led to as much benefit as those with longer durations.⁶

Importantly, it is not only patients with classic claudication symptoms that benefit from supervised treadmill exercise. Two randomized controlled trials of supervised treadmill exercise included patients with and without classic claudication symptoms, and patients without classic claudication also increased treadmill walking time and 6 minute walk distance.^{9,10}

1.3. Home-Based Exercise for Peripheral Artery Disease

Despite the benefits of supervised treadmill exercise, many patients do not participate. Supervised treadmill exercise requires patients to travel to a qualified exercise center three times per week, and though Medicare covers supervised treadmill exercise, patients with PAD tend to be older and have functional limitation,¹¹ and struggle with transportation and logistics. In a

systematic review of patients with PAD eligible for supervised exercise, 50% of patients refused participation and a further 19% reported that attending supervised exercise sessions would be too inconvenient.¹² A home-based walking intervention is likely to be more accessible to patients with PAD, and such interventions have been tested in 5 randomized controlled trials.

Gardner et al. randomized patients with PAD and intermittent claudication to either supervised treadmill exercise (3 times/week, 40 minutes per session, moderate to high intensity), home-based exercise, or control.¹³ Participants randomized to home-based exercise were instructed to walk for 45 minutes, 3 times/week, at their own pace. They wore activity monitors to track exercise, and returned to the center every 2 weeks to meet with an exercise physiologist, review their progress, and set goals for the next 2 weeks. Both supervised treadmill exercise and home-based exercise increased maximal and pain-free walking distance at 12 weeks' follow-up compared with control.

In a similar study, Gardner et al. again randomized patients to traditional supervised treadmill exercise, home-based exercise, or an upper extremity exercise control.¹⁴ Patients randomized to home-based exercise returned to the study center at 1, 4, 8, and 12 weeks for face-to-face meetings with an exercise physiologist to review their progress and set goals for the next 3-4 weeks. Both the supervised treadmill exercise group and the home-based exercise group increased treadmill walking time and 6 minute walk distance compared with control at 12 month follow-up, with the home-based walking group actually increasing 6 minute walk distance by more than the supervised treadmill exercise group.

The Group Oriented Arterial Leg Study (GOALS) randomized patients with PAD to a group-mediated cognitive behavioral theory intervention or an attention control group.¹⁰ Patients in the group-mediated cognitive behavioral theory arm met with other patients with PAD and a coach on a weekly basis, and spent 45 minutes discussing topics such as goal-setting, self-monitoring, and overcoming obstacles to home-based exercise, and then another 45 minutes walking around a track. Compared with control, the group-mediated cognitive behavior theory intervention arm increased treadmill walking distance, 6 minute walk, and other patient-reported measures of quality of life and functional capacity at 6 month follow-up.

Another trial, which enrolled patients with diabetes mellitus and PAD randomized patients to a group behavioral intervention similar to that studied in the GOALS trial versus attention control. Unlike the GOALS trial, this study did not show an improvement in treadmill walking distance.¹⁵

Though these trials tested home-based walking interventions, all required participants to come to in-person visits at least every 3 weeks, and most required at least weekly in-person visits. By contrast, the HONOR clinical trial tested a home-based walking program that included weekly visits during the first month of therapy, during which patients walked for exercise and were assisted with setting goals for exercise, followed by 8 months of a wearable monitor and telephone coaching.¹⁶ The coach called participants weekly during the beginning of the study with gaps between calls gradually increasing to one month. Participants wore a FitBit monitor during the study, and the coach had access to FitBit data, which was used to help patients set goals for future exercise. At the end of 9 months, there was no difference between patients

randomized to the home-based walking intervention and the control arm on treadmill walking distance, 6 minute walk, or patient-reported measures of quality of life and functional capacity. The failure of the truly home-based walking intervention to change patients' behavior is consistent with multiple prior failures of workplace wellness programs and health and fitness apps to change participants' behavior: In all cases, the interventions have not appropriately leveraged principles from theories of health behavior.^{17,18}

1.4 Behavioral Economic Approaches to Encouraging Physical Activity

In a recent clinical trial, a gamification intervention, leveraging insights from behavioral economics, successfully increased physical activity among overweight and obese adults compared with goal-setting alone.¹⁹ In STEP UP, obese and overweight adults were provided with wearable fitness trackers and randomized to one of four interventions to increase physical activity: Goal-setting alone or goal-setting plus one of 3 different gamification strategies. In all arms, participants' baseline daily step count was determined using the wearable fitness tracker during the study's first two weeks, and then participants set a goal of increasing step count by 33, 40, or 50% over the next 6 months. In the gamification arm, participants participated in an intervention that employed behavioral economic principles to increase physical activity, in addition to goal setting.

Specifically, all three gamification interventions leveraged four key behavioral economic concepts, and participants were randomized to one of 3 additional strategies. First, participants signed a precommitment pledge to strive to achieve their goal, and participated in a ramp-up period, during which their daily step goal target increased gradually. Precommitment has been shown to motivate behavioral change, and the ramp-up period provides patients with achievable, incremental improvements.²⁰ Second, the gamification intervention leveraged prospect theory and loss framing, by providing patients with 70 points every Monday, and taking away 10 points each day if they failed to meet their daily step goal target.²¹ Third, the gamification intervention leveraged the fresh start effect by giving participants a fresh set of 70 points each week.²² Fourth, the gamification intervention leveraged achievable goal gradients, social status, and progression through the game by having patients move up or down through five levels at the end of each week based on the number of points they have accrued that week. All gamification intervention arm patients were further randomized into competition, cooperation, and support arms. In the competition arm, participants were put into a group with 2 other study participants, and could access a leaderboard that showed their relative progress versus the other 2 participants. In the cooperation arm, participants worked together in teams of 3, and a team member was randomly selected to represent the team for each day, making each team member accountable to the others. In the support arm, participants provided researchers with the email of a close friend or family member, who received weekly updates on the participants' progress. Each of the 3 behavioral economic-enhanced gamification interventions increased step count from baseline until 6 month follow-up more than goal-setting alone, demonstrating the power of such approaches to help participants increase physical activity.

1.5 Rationale for the GAME PAD Study

The STEP UP study showed the utility of gamification and behavioral economics to increase physical activity, succeeding in circumstances where interventions that did not leverage behavioral economic principles had previously failed. Prior studies of home-based exercise have either required frequent study center visits or have not been effective; however, these programs

that have not employed behavioral economic principles. This study seeks to test whether gamification and behavioral economic principles can be leveraged in a successful, fully home-based exercise program for patients with PAD.

2. Study Objectives

[figure not shown]
The objectives of this study are the following:

1. To test the effectiveness of a gamification-enhanced home-based walking program, as compared with a home-based walking program using goal-setting and automated coaching alone, to improve walking endurance in patients with peripheral artery disease
2. To identify psychometric features associated with response to gamification in patients with peripheral artery disease

3. Study Design

3.1. General Overview

The GAME PAD study is a two-arm randomized controlled trial aimed at evaluating whether a home-based walking program with automated coaching augmented with gamification and behavioral economic principles improves functional capacity in patients with PAD. The study will randomize 100 patients with PAD to a 16-week home-based walking program using goal-setting alone (attention control) or to the same home-based walking program with automated coaching augmented with gamification and behavioral economic principles. There will be a 2-week run-in period to obtain baseline measures of physical activity, followed by a 16-week intervention period, and an 8-week follow-up period (see study protocol figure below).

The study will be conducted using Way to Health, a research information technology platform at the University of Pennsylvania used previously for physical activity behavioral interventions.

After institutional review board (IRB) approval of the study, patients who meet the eligibility criteria will be contacted by email, phone call or letter to invite them to participate. Those who

qualify and express interest will provide online informed consent to the study procedures. All patients will receive a wearable activity tracker (Fitbit Inspire) that will be enrolled in the Way to Health platform. The Fitbit and Way to Health platform will continuously track patients' steps and survey patients regarding pain with walking monthly. Within the Way to Health platform, patients will be randomized to one home-based exercise program or the other. All other management decisions are completely at the discretion of the care providers. Data capture will include:

- **Baseline case report form** (for each patient) collecting clinical information abstracted from the medical record
- **Patient-reported quality of life and functional limitation related to PAD** collected via telephone survey and/or the Way to Health platform at the time of enrollment and at 16- and 24-week follow-up
- **Psychometric features** collected via in-person survey at the time of enrollment
- **Daily step count** and calculated **exercise minutes** collected via FitBit charge
- **Patient-reported pain with ambulation** collected via the Way to Health platform at monthly intervals

3.2. Site

GAME PAD will enroll patients from the University of Pennsylvania Health System, which consists of five large hospitals including the Hospital of the University of Pennsylvania, Penn Presbyterian Medical Center, Pennsylvania Hospital, and Chester County Hospital, and from Cardiovascular Solutions of Central Mississippi, a private cardiovascular practice primarily serving a socioeconomically depressed region. Regardless of site, all patients will be consented and trial participation will be managed virtually through the Way to Health platform by study staff from the University of Pennsylvania, and no clinical personnel from any site will participate in research procedures or have access to any participant data.

3.3. Patient Selection Criteria

3.3.1. Inclusion Criteria

Patients are eligible to be included in the study if they are ≥ 18 years of age and meet all of the following criteria:

1. Peripheral artery disease, defined as ankle-brachial index < 0.90 , lower extremity CT scan or ultrasound consistent with PAD, angiography with $\geq 70\%$ stenosis in any lower extremity artery, or a history of medical or surgical revascularization
2. Owns a smartphone or tablet operating the iOS or Android operating system

3.3.2. Exclusion Criteria

Patients are excluded if they meet any of the following criteria:

1. Unable or unwilling to provide informed consent, including but not limited to cognitive or language barriers (reading or comprehension)
2. Critical limb ischemia, defined as rest pain, ulceration, or tissue loss involving the lower extremity
3. Planned lower extremity revascularization
4. Prior above or below the knee amputation
5. Require a wheelchair or the use of a walking aid other than a cane
6. Currently participating in a supervised exercise program for patients with PAD

7. Anticipated life expectancy less than 6 months
8. Any other reason why it is not feasible to complete the entire 6-month study
9. Step count > 7500/day during the baseline data collection period

4. Study Procedures

4.1. Screening and Informed Consent

Patients with peripheral vascular disease will be identified within the electronic health record and Penn Data Store, the health system's clinical data warehouse, by ICD-10 codes consistent with peripheral artery disease (I70.2x, I70.3x-I70.7x, I73.9) or peripheral artery disease on their problem list. They will be invited to participate by email, and will be randomized to opt-in or opt-out approaches. Patients randomized to the opt-in approach will be instructed to call a study coordinator or visit the Way to Health platform to enroll in the study; patients randomized to the opt-out study will be notified that they will be called by a study coordinator unless they decline to participate. This sub-study will be detailed in a separate protocol. Potentially eligible patients may also be identified by their cardiologist or vascular surgeon when seen in clinic, and directed to contact the study team or to visit the study website to learn more and enroll. These patients will not be included in the opt-in versus opt-out substudy.

Interested patients will visit the study website on the Way to Health platform to learn more about the study, create an account, provide informed consent, and complete initial baseline eligibility surveys. Study coordinators will be available to assist patients with this process, as necessary.

We will follow an IRB-approved approach taken by many studies using the Way to Health platform to obtain informed consent. Upon reaching the portal, potential participants will be asked to create an account and will then be informed of the details of the study, including its objectives, duration, requirements, and financial payments. The Way to Health portal will then take interested participants through an online informed consent. The consent document will be divided into sections and potential participants will have to click a button to advance through each section. This is to help ensure that participants read the consent form thoroughly by breaking down the form into manageable blocks of text. Each section will have a button allowing the user to contact a researcher via email or by telephone if they have questions about the consent form. Successive screens will explain the voluntary nature of the study, the risks and benefits of participation, alternatives to participation, and that participants can withdraw from the study at any time. On the final consent screen, potential participants who click a clearly delineated button stating that they agree to participate in the study will be considered to have consented to enroll. Participants will be provided with details regarding how to contact the research team via email or phone at any time if they subsequently wish to withdraw from the study. This contact information will remain easily accessible via the participants' individual Way to Health web portal dashboards throughout the study.

Support partners will provide verbal informed consent via telephone for their name, email address, and phone number to be stored in the study database.

4.2. Baseline Questionnaire

After providing informed consent, participants will complete an online questionnaire to confirm eligibility and complete the study surveys.

The baseline survey will consist of the San Diego Claudication Questionnaire and the Walking Impairment Questionnaire to characterize limb symptoms and functional limitations,^{23,24} the Patient-Reported Outcomes Measurement Information System (PROMIS) measures of mobility, pain interference, and satisfaction with social roles and activities,²⁵ and the SF-36 physical functioning scale.²⁶ Patients will also complete several questionnaires to obtain a psychometric profile: the Big Five Inventory survey to evaluate personality characteristics, the Grit Scale to assess perseverance, the Self Efficacy for Exercise Behaviors survey, the PHQ-9 questionnaire to assess mental health state, and the MOS Social Support survey.

4.3. Determination of Baseline Step Count and Goal-Setting

Eligible participants will be mailed a wearable activity tracking device to wear for about two weeks to collect a baseline step count. They will also receive an email with baseline information about home-based exercise in PAD, including information about the benefit of walking in relieving PAD symptoms and improving functional capacity, and instructions for exercise in PAD.

The patients will be told to wear the device for two weeks to get accustomed to it. During this period, we will use a protocol from prior work to estimate a baseline step count using the second week of data. The first week of data will be ignored to diminish the tendency for use of devices in week 1 of receiving a new device to be significantly higher than what might be observed at steady state. To prevent risk of mismeasurement, we will ignore any daily values less than 1000 steps because evidence indicates these values are unlikely to represent capture of actual activity.^{27,28} At least four days of data must be available during that second week to estimate baseline measures; otherwise the period will be extended, and patients will be called to inquire if there are any issues with using the device. In prior work, we typically have 6 to 7 days of data from more than 90% of participants.²⁹ Participants who do not complete this run-in phase will not be randomized into the trial, nor will patients with step counts > 7500 steps/day during the run-in phase.

Once baseline measures have been established, eligible participants will be contacted to choose their goals using an approach we have found to work well in previous studies. They will be given their baseline step count and asked to select a step goal increase of 33%, 40%, 50% or choose a custom goal as long as it is at least 1500 steps greater than baseline. We have used this approach in the past because it gives participants the options of setting their own goal but also steers people to choose one of the options provided, any of which would be terrific from the standpoint of increasing physical activity. Leaving it completely open-ended risks having participants either pick goals that are ‘too easy’ or not likely to be attainable. In prior work, we find that on average participants chose ambitious goals and more than half selected a 50% step increase.

To achieve their goal, patients will be recommended to begin walking for 15 minutes daily at their own pain-free pace or with minimal pain, gradually increasing the duration to 30-60 minutes daily, and to stop and rest if the pain becomes more significant, and then resume walking.

4.4. Randomization

Participants that have established baseline measures and finished goal selection will be randomly assigned to attention control or the automated coaching + gamification intervention using a 1:1 allocation and stratifying on baseline step count (< 2500 steps, 2500 – 5000 steps, > 5000 steps)

with block randomization and block sizes of 2 using an electronic number generator through the Way to Health research technology platform.

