4) Supportive sponsor: Each participant will select a family member or friend of their choice who will serve as a supportive sponsor. This person will receive a weekly email with the participant's progress including accumulated points, level in the game, and average step count. This supportive sponsor will help to enhance social incentives to motivate the individual towards his or her goal. We will encourage participants to select someone with whom he or she comes into frequent contact and is close to such as a partner, family member, or friend that they see often. Prior to starting in the study, we will conduct a three-way phone call with the participant and their supportive sponsor. We will provide an overview of study procedures for their arm assignment, and then prompt the participant and supportive sponsor to discuss ways in which they can help the participant meet their step goals. At least 3 goals will be decided upon during the conversation, and if needed, we will provide suggestions for supporting the participant. The goals that are decided upon will be entered into a survey by study staff, and will be included in weekly emails to the supportive sponsor. After 8 weeks, we will reach out to the participant and supportive sponsor if the participant is stuck in lower levels of blue or bronze to determine if changes should be made to the original support goals. Participants without a supportive sponsor will not be excluded from study participation, and will complete a slightly modified version of the baseline and 8-week phone call, if necessary, in two-way conversations with study staff.

The intervention will end after 16 weeks, but participants will continue to receive a daily text message stating whether they achieved their step goal on the prior day during the 8 week follow-up period.

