regression models to evaluate changes in physical activity outcomes measures adjusting for each participant's baseline step, time at the observation level using calendar month fixed effects, participant random effects, and adjusting for repeated observations of participant step counts. We will compare changes in daily step count and physical activity from baseline to the intervention period, excluding weeks 1-4 (the ramp-up period). We will repeat these analyses, comparing changes in daily step count and physical activity from baseline to the follow-up period. Secondary analyses will fit mixed effects regression models adjusted for other variables of interest such as participant characteristics. Exploratory analyses will fit mixed effects regression models to evaluate associations of participant characteristics or behaviors with strong or poor performance in the outcome measures. In a subgroup analysis, we will separately analyze subgroups reporting and not reporting exertional lower extremity symptoms.

For changes in survey measure scores from baseline to the end of the intervention, and from baseline to the end of follow-up, we will compare the intervention and control arms using paired t-tests, without adjustment for baseline characteristics.

6. Human Research Protection

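### Fixed blocks of 2 within the baseline-step strata make about half of the allocations knowable in advance to anyone who follows a stratum's sequence; varying, undisclosed blocks are a cheap improvement.

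*Combined protocol and SAP*

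**What the plan says.** Section 4.4 sets 1:1 allocation in three strata of baseline step count (below 2500, 2500 to 5000, above 5000), "with block randomization and block sizes of 2 using an electronic number generator through the Way to Health research technology platform". Site is not a stratum. The block size is given as a single number, and no section says that it varies, that it is withheld, or who can see past assignments.

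The surrounding procedures bear on who could use this:

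- Section 3.2: for both sites, "trial participation will be managed virtually through the Way to Health platform by study staff from the University of Pennsylvania". Clinical personnel at the sites have no research role and no data access.
- Section 4.3: "Once baseline measures have been established, eligible participants will be contacted to choose their goals". The stratum is therefore known at this contact.
- Section 4.4 places assignment after that contact: "Participants that have established baseline measures and finished goal selection will be randomly assigned to attention control or the automated coaching" arm.
- Section 4.5.2 describes a call with the intervention participant and the supportive sponsor: "We will provide an overview of study procedures for their arm assignment". It adds: "The goals that are decided upon will be entered into a survey by study staff". No comparable control-arm call is described.
- Section 3.3.2, exclusion 8, is open-ended: "Any other reason why it is not feasible to complete the entire 6-month study".
- Section 6.6.1 keeps the arms under code letters until the analysis is complete. That cannot hide the arm from whoever makes an arm-specific call.

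**The concern.** Concealment means that nobody who can influence whether, when or how a patient enters knows the next assignment. A printed, fixed block of 2 gives this up for every second patient in a stratum, provided someone follows the sequence. One team manages everyone, and no separation is described between staff who make contact before randomization and staff who make the sponsor calls.

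Foreknowledge could act only between the moment the stratum is known and the moment of randomization. That leaves three openings:

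1. the goal-setting contact, which matters because the intervention arm's ramp-up and daily targets are computed from the chosen goal;
2. a late use of exclusion 8;
3. the order in which ready patients of one stratum are randomized, which needs at least two pending.

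If any of these were used, the arms could differ in motivation, symptoms or support, none of which is in the primary model. The random number generator makes the sequence fair; it does not make the second member of a pair unpredictable.

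**Working it through.** The documents give no figure for predictability, so there is none to reproduce. Inputs: block size 2, 1:1 allocation and three strata (section 4.4); 100 patients (section 5.2). The stratum sizes are not given. The exact results below hold for every split. The simulations assumed splits of 31/42/27, 34/33/33, 20/50/30 and 21/46/33.

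**Blocks of 2, count and last assignment known.** In a stratum of n patients, floor(n/2) allocations are fixed in advance. Because 100 is even, either none or two of the three strata are odd:

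- none odd: 100/2 = 50 certain;
- two odd: (100 − 2)/2 = 49 certain.

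The best guess is right for all certain allocations and half of the rest: 50 + 50/2 = 75, or 49 + 51/2 = 74.5, of 100.

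**Blocks of 2, last assignment only, position unknown.** The opposite arm has probability 0.5 × 1 + 0.5 × 0.5 = 0.75. Nothing is certain.

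**Blocks of 2, sequence followed, position unknown at the start.** The same arm twice running can occur only across a block boundary, so the first repeat reveals the position.

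- If observation starts at a block's first patient, the repeat comes at observation 3, 5, 7, … with probabilities 1/2, 1/4, 1/8, …, on average at 3 + 2 = 5.
- If the first patient was missed, it comes at 2, 4, 6, …, on average at 2 + 2 = 4.
- Until then the observer loses on average 1 × 1/2 + 2 × 1/4 + 3 × 1/8 + … = 2 otherwise known allocations per stratum, or 6 over three strata.
- 49 or 50 less 6 gives 43 or 44 certain. Simulation (20,000 runs per split) gave 43.0-44.0, 5th to 95th percentile 38-47, and best guess 72.0-74.5%.

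**Other block schemes.** For a complete fixed block of size 2m, the expected share certain is 1/(m + 1).

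| Scheme | Certain | Best guess |
|---|---|---|
| Fixed 2 (complete blocks) | 1/2 = 50% | 75% |
| Fixed 4 (complete blocks) | 1/3 = 33.3% | 70.8% |
| Fixed 6 (complete blocks) | 1/4 = 25% | 68.3% |
| Mixed 4/6, perfect tracker who knows the sizes | about 6 of 100 | about 69% |
| Mixed 4/6, running imbalance only | about 1 of 100 | not computed |

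The mixed rows are simulated with the two sizes equally likely. A separate simulation with a full probability filter also gave about 6% and 69%.

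**Cost in balance.** With mixed 4/6 blocks a stratum can be off by at most 3. At exactly 100 the maximum is 3 + 3 + 2 = 8, since at most two strata are odd; with an odd total it is 9. The simulated mean absolute difference was 1.1-1.3, 95th percentile 4. Blocks of 2 give at most 2 at exactly 100.

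Standard-error inflation at a difference of 9: √[(1/54.5 + 1/45.5)/(2/50)] − 1 = √(0.04033/0.04) − 1 = 0.4%.

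Power for 1100 steps at SD 2000 (two-sided 0.05, normal approximation): at 50/50, 1100/(2000 × √(2/50)) = 2.75, and Φ(2.75 − 1.96) = 78.5%. At 53/47 it is 78.4%, and at 54/46 it is 78.3%.

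**The case against.** The strongest reply is that the observer is assumed. To reach about half, one person must know every assignment, by stratum and in order. The documents show staff learning the arm only through the intervention-arm call, so control status must be deduced, and silence about separate staff does not prove that there are none. This stands: 49-50 is the figure under full tracking, and 43-44 still supposes that each assignment is followed.

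The openings can also be disputed. Section 4.2 confirms eligibility straight after consent, and section 4.3 sends the tracker only to eligible people, which puts the main eligibility check before the stratum is known. That weakens the exclusion 8 route without closing it. The criterion has no time limit, and exclusion 9 is itself applied after the run-in, so the list is not closed at section 4.2. Section 4.3 does not say that a person conducts the goal-setting contact, and participants choose the goal. No queue of pending patients is described.

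Several features limit harm: electronic assignment, consent before the run-in, a tracker outcome, intention-to-treat analysis, and a primary model that adjusts for "baseline step, time at the observation level using calendar month fixed effects". They reduce the likely damage. Tracker measurement does not, however, govern who is randomized, in what order or with what goal, and baseline steps are only one covariate.

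Finally, the remedy is partial, because best-guess accuracy falls only from about 75% to about 69%. This is correct. What the change removes is certainty.

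**Conclusion.** The concern holds as an avoidable weakness in allocation concealment and should be corrected. Under section 4.4 as written, 49 or 50 of 100 allocations are determined for someone who knows each stratum's count and last assignment, and about 43-44 for someone who follows the assignments without knowing the block position. Access to the sequence is plausible for the central team, given sections 3.2, 4.3 and 4.5.2, but it is not stated. No bias is shown, and its size in steps/day cannot be derived from the documents. The exact count does not depend on the stratum sizes; the simulated figures rest on the assumed splits and, for mixed blocks, on equally likely sizes. Confidence is medium because the practical exposure depends on staffing and platform access that the documents do not describe.

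**What to change.** In section 4.4, specify randomly varying permuted blocks (for example 4 and 6) within the three baseline-step strata, and keep the block sizes in a document that enrolling staff do not see. Keeping past assignments from staff who make contact before randomization would add protection, since varying blocks alone leave the best guess at about 69%.

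The cost is one sentence and a new allocation set-up for blocks not yet opened, with no extra patients, visits or data. The documents do not describe the platform's randomization set-up, so a small technical effort is an assumption. The statistical downside is the slightly larger possible arm imbalance worked out above.
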